12.0 Waiver of Consent/Authorization for Recruitment Purposes

This section is required when medical records may be reviewed to determine eligibility for recruitment.

12.1 * PRACTICABILITY OF OBTAINING CONSENT PRIOR TO ACCESS: Study personnel need to access protected health information (PHI) during the recruitment process and it is not practicable to obtain informed consent until potential subjects have been identified: (REQUIRED)

- Yes

If **no**, a waiver of consent/authorization is NOT needed.

12.2 * RISK TO PRIVACY: A waiver for screening of health records to identify potential subjects poses no more than minimal risk to privacy for participants:

- Yes

If **no**, a waiver of authorization can NOT be granted.

12.3 * RIGHTS/WELFARE: Screening health records prior to obtaining consent will not adversely affect subjects' rights and welfare:

- Yes

If **no**, a waiver of authorization can NOT be granted.

12.4 * IDENTIFIERS: Check all the identifiers that will be collected prior to obtaining informed consent:

- Names
- Dates
- Postal addresses
- Phone numbers
- Fax numbers
- Email addresses
- Social Security Numbers*
- Medical record numbers
- Health plan numbers
- Account numbers
- License or certificate numbers
- Vehicle ID numbers

- Device identifiers or serial numbers
- Web URLs
- IP address numbers
- Biometric identifiers
- Facial photos or other identifiable images
- Any other unique identifier
- None

Note: HIPAA rules require that you collect the minimum necessary.

12.5 * HEALTH INFORMATION: Describe any health information that will be collected prior to obtaining informed consent:

Information about potential participants including age, whether or not they meet criteria for PCOS and hyperandrogenism, as well as blood test review (which may include total and free Testosterone, estradiol, Luteinizing Hormone (LH), Follicle Stimulating Hormone (FSH), insulin, hemoglobin A1c, fasting serum glucose, lipid panel, and sex hormone binding globulin levels), as well as medication history if available will be collected prior to obtaining informed consent.

Note: HIPAA requires that you collect the minimum necessary.

12.6 * DATA RETENTION/DESTRUCTION PLAN: Describe your plan to destroy any identifiable data collected to determine eligibility for recruitment. This should be done at the earliest opportunity. If you plan to retain identifiable recruitment data, provide the justification for doing so:

Any paperwork with identifiable data regarding potential participants in the study used to determine eligibility will be destroyed using the secured shredder boxes located in clinic immediately after the patient's second clinic visit (as after this time point patients will have either consented to the study or not).

All baseline blood work is typically done prior to clinic visit and so no blood samples will be collected or stored in the clinic for this study or recruitment purposes. Recruitment data for the study (questionnaires, blood work, pelvic ultrasound findings and modified Ferriman-Gallwey scores) are all stored on REDCap on a secured network. Any information with identifiable information that is obtained on paper will be inputted into REDCap and copies destroyed thereafter.

13.0 Risks and Benefits

13.1 RESEARCH-RELATED RISKS: Check if your study involves any of these specific research-related risks to participants that may need to be disclosed in the consent form:

- For interventional studies, risk that the regimen may be more harmful or less effective than other available interventions
- Risks associated with radiation exposure for imaging studies specifically for research purposes
- Risks associated with the administration of contrast agent for imaging studies
- Risks associated with withholding of treatment or discontinuation of current treatment (e.g., washout period is required by the study protocol)
- For randomized, placebo-controlled trials, possible temporary or permanent health consequences from the deprivation of effective therapies during the placebo administration period
- For studies involving a sham surgical procedure, the risk that participants may experience increased morbidity without the possibility of benefit
- Risks associated with modification or extension of a surgical procedure primarily for research purposes (e.g. risks associated with prolonging anesthesia, time in the operating room, etc.)
- Risk of pain or physical discomfort caused by the research intervention

Possible personal discomfort due to sensitive topics (stress, embarrassment, trauma)

13.2 RISKS: Describe any anticipated risks and discomforts not listed above:

Aside from the above mentioned risks, participants may be at risk for any of the number of adverse side effects that are seen with OCP therapy (listed below).

Likely side effects: Premenstrual syndrome (13.2%), headache/migraine (10.7%), breast pain/tenderness/discomfort (8.3%), nausea/vomiting (4.5%), abdominal pain/tenderness/discomfort (2.3%), mood changes (2.3%).

Less likely side effects: Gallbladder disease, hypertension, hepatic adenomas, elevation in lipid levels

Rare but serious side effects: Venous thromboembolism (risk is greatest during the first year of use and less than the risk associated with pregnancy), hepatocellular carcinoma. Women over 35 years of age who smoke have an increased risk of serious cardiovascular events from OCP use including heart attack, blood clots or stroke.

Side effects specific to Yasmin: There may be a slight increase incidence of Deep Vein Thrombosis (a very rare side effect of all OCPs) for Yasmin as compared to some other OCPs.

Randomization risks: Subjects will be assigned to a treatment program by chance, and the treatment the subject receives may prove to be less effective or to have more side effects than the other study treatment or other available treatments. Subjects assigned to the continuous OCP treatment group are likely to have more irregular bleeding than those randomized to cyclical use.

Blood drawing (venipuncture) risks: Drawing blood may cause temporary discomfort from the needle stick, bruising, infection and fainting.

Pelvic Ultrasound risks: There can be some discomfort and or pressure experienced with the pelvic ultrasound as this is done transvaginally.

Questionnaires: Several of the questionnaires ask detailed questions regarding the participants mental health (anxiety, depression), and quality of life regarding the diagnosis of PCOS and how it may or may not cause some distress or discomfort. If a subject is identified to be at risk or currently reporting suicidality, following the study protocol, the investigator as well as a dedicated psychologist will be notified and will determine if that patient should be placed on a secured medical hold (likely taken to an Emergency Room for further evaluation). Details of the protocol are located in the CCOUP Study Suicide Ideation Protocol.

13.3

MINIMIZING RISKS: Describe the steps you have taken to minimize the risks/discomforts to subjects. Examples include:

- **designing the study to make use of procedures involving less risk when appropriate**
- **minimizing study procedures by taking advantage of clinical procedures conducted on the study participants**
- **mitigating risks by planning special monitoring or conducting supportive interventions for the study**
- **having a plan for evaluation and possible referral of subjects who report suicidal ideation**

As we do not anticipate significant changes in hormone levels each month, we have limited blood draws to 1 month, 3 months and 6 months post start of OCP therapy; thereby reducing procedures that may cause distress and or pain to the participant. While there are a number of adverse side effects associated with OCP therapy (Yasmin) this is the same as what would be expected if they were not in the study and started on the medication for management of anovulation or contraception in PCOS. If an adverse reaction were to take place, procedures will

be set in place for participants to contact the study team and determine if this was in fact related to the medication. In the event that there is a true drug reaction, we would immediately stop the patient from continuing this mediation.

13.4 RESOURCES: Describe the resources in place to conduct this study in a way that assures protection of the rights and welfare of participants: These resources typically include appropriately trained and qualified personnel (in terms availability, number, expertise and experience), funding, space, equipment, and time to devote to study activities. Depending on the nature of the research study, investigators should consider the proximity or availability of critical resources that may be essential to the safety and welfare of participants, such as

- the proximity of an emergency facility for care of participant injury
- availability of psychological support after participation
- resources for participant communication, such as language translation services

Information will be provided in the consent forms that includes contact information for participants to call in if they have questions regarding the study or their rights.

13.5 * BENEFITS: (REQUIRED) Note: These are the benefits that the IRB will consider during their review. They are not necessarily appropriate to include in the consent form.

Possible immediate and/or direct benefits to participants and society at large (check all that apply):

Positive health outcome (e.g. improvement of condition, relief of pain, increased mobility, etc.)

Closer follow-up than standard care may lead to improved outcomes or patient engagement

Health and lifestyle changes may occur as a result of participation

Knowledge may be gained about their health and health conditions

Feeling of contribution to knowledge in the health or social sciences field

The research presents a reasonable opportunity to further the understanding, prevention, or alleviation of a serious problem affecting the health or welfare of children

Other benefit (describe below)

None

13.6 RISK TO BENEFIT RATIO: Explain why the risks to subjects are reasonable in relation to anticipated benefits, if any, to the participant or society:

Participants in this study will be provided with current standard of care therapy for PCOS. The only difference is that they may have more frequent blood draws to check hormone levels and will have a re-evaluation of the hirsutism and ovarian morphology at the end of the study.

14.0

Data and Safety Monitoring Plan

14.2 * DATA AND SAFETY MONITORING PLAN: (REQUIRED)

All greater than minimal risk studies are required to provide a plan. Lack of an adequate plan is one of the most common reasons why IRB approval is delayed.

Instructions:

Describe the plan for monitoring data quality and participant safety. Key areas that should be included in the plan are:

- An explanation of the plan to monitor data collection, study progress, and safety
- A description of who will perform the monitoring and at what frequency (e.g., the PI only, a contract research organization, a Data and Safety Monitoring Board or Data Monitoring Committee, etc.)
- The type of data and events that will be reviewed (e.g., adverse events, breaches of confidentiality, unanticipated problems involving risk to participants or others, unblinded efficacy data, etc.)
- Procedures and timeline for communicating monitoring results to the UCSF IRB, the study sponsor, and other appropriate entities
- Assurance that the research team will adhere to the **UCSF IRB reporting requirements**

As appropriate:

- A plan for conducting and reporting interim analysis
- Clearly defined stopping rules
- Clearly defined rules for withdrawing participants from study interventions

Internal (on-site) Adverse Events: These will be monitored by the PI who will determine whether a definite, probable or possible related AND serious or unexpected event has occurred. If an event has occurred it will be reported within 5 working days of PI's awareness or immediately (in the event of related deaths or life-threatening events) using the iRIS Adverse Event Reporting Form.

Monitoring of data collection and study progress: This will be performed by the study investigator along with the PI every 2 weeks with a chart review of the current enrolled participants to ensure labs, questionnaires and procedures have been done in a timely manner in accordance to the protocol, there are no breaches of confidentiality or unanticipated problems involving risk to participants or others if an adverse event has occurred.

Trial Stopping Rules: In the event that a rare but serious side effect such as a thromboembolism or hepatocellular carcinoma occurs within multiple subjects within a study group, the PI will investigate this adverse event (AE) to determine the safety of continuing the trial further. As this pilot study will be recruiting individuals over a long period of time, the PI and investigators will meet to discuss on an on-going basis patient AE to determine if there is a need to stopping the trial due to patient safety concerns.

A suicidal ideation and depression protocol has also been set in place in case a patient is found to have answered Question 9 of the BDI-II surveys with a score greater than zero or a total score over 19. The protocol details specific steps that need to be taken immediately including contacting [name] and following up with the patient immediately. Details of the protocol have been attached to this application as a separate document.

14.3 * DATA AND SAFETY MONITORING BOARD (DSMB): Will a Data and Safety Monitoring Board (DSMB) be established: (REQUIRED)

Yes
 No

Guidelines

A Data and Safety Monitoring Board (DSMB) or Data Monitoring Committee (DMC) is a formal, independent committee that is specifically established to conduct interim monitoring, oversight and analysis of study information and data to assure the continuing safety, efficacy, appropriateness, relevance,

and integrity of the study.

The UCSF IRB reserves the right to request a DSMB/DMC for any study. However, the following are factors that the IRB will consider when making this determination:

- There is a significant likelihood of a serious adverse event to subjects
- The study is conducted at multiple sites and the level of risk is greater than minimal
- The study generates data that are blinded or randomized
- The study involves a large number of patients randomized to one of two or more interventions
- A study for which the performance of an interim analysis is crucial for the protection of the subjects
- First use in humans
- First use in children
- The study involves gene transfer, stem cell therapy, or other novel interventions for which long-term outcome data are not known or available

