This is a pilot, randomized, open label clinical trial looking at the effects of different formulations of combined oral contraceptive pills (OCP) provided in therapy following the diagnosis of PCOS. Participants will be randomized in a 1:1 ratio to receive either a 21 day active hormone/7 day placebo pill pack (cyclical OCP) or an 168 day active hormone pill pack (6 month continuous OCP) and monitored with blood work and physical exams over the course of 6 months. Both groups will receive the same combined OCP component, containing 30mcg of ethinyl estradiol and 3 mg of Drospirenone (Yasmin).

7.5 BACKGROUND AND SIGNIFICANCE: Briefly provide the background and significance of this study (e.g. why is this study needed) (space limit: one half page):

If this is a first in humans study, please summarize the safety data from the animal studies. For pediatric drug or device studies, please identify if this is the first study in pediatric populations.

Polycystic Ovary Syndrome (PCOS) is a complex endocrine disorder that affects 5-15% of women worldwide¹ and is associated with multiple comorbidities such as obesity, Type 2 Diabetes, infertility and cardiovascular events^{2,3}. In the US, it is the most common endocrine abnormality of reproductive-aged women³. While the underlying cause remains unclear, women with PCOS are often found to have anovulatory cycles (menstrual dysfunction), clinical or biochemical signs of hyperandrogenism (such as elevated Testosterone levels, or male pattern hair growth and acne), and/or excessive follicle counts on ultrasound of the ovaries. Based on the Rotterdam Criteria (established in 2003) two out of the three above criteria must be met to diagnose PCOS⁴. While other definitions exist, the Rotterdam Criteria is widely used as an established diagnostic tool.

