At 3 months into therapy, participants will come back to the PCOS clinic for routine care follow up and be seen by a Reproductive Endocrinology and Fertility specialist. This visit is considered routine and not specific to the study. However, during this visit a study investigator will also touch base briefly with the participants to see how they are doing. Four online surveys (through REDCap) will also be sent to participants that addresses if they have missed any doses of their medication, assess their quality of life, acne changes, screen for anxiety and depression. Patients will be asked to complete the BDI-II survey on their clinic day so that it can be evaluated by the study team immediately in the event that there are concerns for suicidal risk. In addition, participants will once again get blood work at their visit (including total Testosterone, SHBG, estradiol, LH, FSH) but will also go to their local lab (covered by their insurance) for additional routine labs including a fasting lipid panel, fasting serum glucose, insulin, and HbA1c. These labs are routinely done with follow up regardless of being in the study and should therefore be covered by each participant's insurance. Once again, the cyclical group should be on placebo/sugar pills at the time of blood draw and the continuous group on active hormone pills.

At 6 months into therapy, participants will come in for a study visit (this is not considered routine care) in which they will have their vitals taken, a physical exam that includes a re-evaluation of their mFG score, and an in-clinic pelvic ultrasound to assess ovarian volume and follicle counts performed by a Reproductive Endocrinology and Infertility specialist. They will also be emailed 5 post-study surveys through REDCap, that includes a quality of life questionnaire for PCOS, acne and hirsutism, as well as anxiety and depression screening, and includes questions regarding any missed doses of their medication. Patients will again be asked to complete the BDI-II survey on their clinic day so that it can be evaluated by the study team immediately in the event that there are concerns for suicidal risk. Lastly, participants will again have blood work drawn in the clinic (total Testosterone, SHBG, estradiol, LH, FSH). These labs are not considered standard of care and will be paid for by the study team.

Participants may also be called emailed reminders for follow up at least 2-3 times during the 6 month period.

CCOUP Study Timeline

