9.0 Sample Size and Eligibility Criteria

9.1 ENROLLMENT TARGET: How many people will you enroll:

60

If there are multiple participant groups, indicate how many people will be in each group:

As this is a pilot study we expect to enroll 30 participants into the cyclical OCP group and another 30 participants into the continuous 6 month OCP group with a total of sample size of 60.

9.3 SAMPLE SIZE JUSTIFICATION: Explain how and why the number of people was chosen. For multi-site studies, this is referring to the number that will be enrolled across all sites:

Since this is a feasibility or pilot study we expect to enroll 30 patients in each treatment arm for a total of 60 participants. Typically 7-9 new patients are seen in the PCOS Multidisciplinary clinic each month, however, due to COVID-19 there were restrictions on the number of individuals seen down to roughly 5-6 new patients are seen in the PCOS Multidisciplinary clinic each month. Now, there are new patients seen each month again. Given the protracted recruitment, any patient on chart review presenting to the Center for Reproductive Health with a complaint of PCOS seeking treatment, will also be considered for the study. **Additionally, all patients who met PCOS criteria in the last 2-10 years and present for a PCOS reassessment will be eligible for enrollment.** Assuming 2-3 outpatients seen in Multidisciplinary clinic and an additional 2-3 outpatients seen at the Center for Reproductive Health will meet criteria to participate in the study and will consent each month, we expect to reach our goal of at least 60 study subjects within the next 6 months.

9.4 * PARTICIPANT AGE RANGE: Eligible age ranges: (REQUIRED)

- 0-6 years
- 7-12 years
- 13-17 years
- 18-64 years
- 65+

9.5 * STUDY POPULATIONS: Data will be collected from or about the following types of people (check all that apply): (REQUIRED)

- Inpatients
- Outpatients
- Family members or caregivers
- Providers
- People who have a condition but who are not being seen as patients
- Healthy volunteers
- Students
- Staff of UCSF or affiliated institutions
- None of the above

9.6 * SPECIAL SUBJECT GROUPS: Check the populations that may be enrolled: (REQUIRED)

- Children / Minors
- Subjects unable to consent for themselves
- Subjects unable to consent for themselves (emergency setting)
- Subjects with diminished capacity to consent
- Subjects unable to read, speak or understand English
- Pregnant women
- Fetuses
- Neonates
- Prisoners

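### Apart from mood, the plan describes no systematic collection or by-arm tabulation of irregular bleeding, the one harm it predicts will differ between arms, or of the common side effects it lists

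*Combined protocol and SAP*

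**What the plan says.** Under randomization risks, section 13.2 makes one prediction of a harm that differs between the arms: "Subjects assigned to the continuous OCP treatment group are likely to have more irregular bleeding than those randomized to cyclical use". It gives no rate and no definition of irregular bleeding. The same section lists six likely side effects with rates: premenstrual syndrome 13.2%, headache or migraine 10.7%, breast symptoms 8.3%, nausea or vomiting 4.5%, abdominal symptoms 2.3% and mood changes 2.3%. It does not say over what period those rates apply.

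Section 7.10 and its timeline set out what is collected:

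- **Month 1:** hormone bloods. No survey is scheduled.
- **Month 3:** bloods, a routine specialist visit, a short informal contact with a study investigator, and online surveys described as something that "addresses if they have missed any doses of their medication, assess their quality of life, acne changes, screen for anxiety and depression".
- **Month 6:** vitals, physical exam with hirsutism score, pelvic ultrasound, bloods, and surveys on PCOS, acne and hirsutism quality of life, anxiety, depression and missed doses.

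Section 13.3 says that, for adverse reactions, procedures will "be set in place for participants to contact the study team and determine if this was in fact related to the medication". Section 14.2 has the principal investigator "determine whether a definite, probable or possible related AND serious or unexpected event has occurred", with events that qualify sent to the IRB within five working days, or immediately if they are related deaths or life-threatening. It also provides for a chart review every two weeks and continuing discussion of adverse events with a view to stopping the trial.

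Section 7.26 plans between-arm comparisons of testosterone, metabolic parameters, and anxiety and depression. It mentions neither bleeding nor adverse events.

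**The concern.** The arms take the same pill on different schedules, so bleeding pattern and minor side effects are a natural part of the comparison. Section 13.2 itself warns participants that their assigned arm may turn out to have more side effects than the other. Bleeding can be measured by arm: the earlier trial in healthy women summarised in 7.6 did so, finding no difference in overall bleeding and fewer moderate or heavy bleeding days on the continuous regimen. That is a different measure from irregular bleeding, so it does not contradict 13.2, but it leaves the question open in women with PCOS.

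Two things are at stake. First, the trial is open label and women are told which arm to expect irregular bleeding in. Whether a woman mentions it then depends on her arm and her expectations as well as on what happened, so counts of spontaneous reports are not a fair comparison. Second, Aim 1 is feasibility. The surveys ask about missed doses, but no described item asks why they were missed. If bleeding or nausea leads women to skip pills or withdraw, the pilot could see the missed doses and not learn the cause.

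**Working it through.** The plan states no tolerability figure, so there is nothing to reproduce. The check has three steps.

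**1. Match each anticipated common effect to a described instrument and a planned comparison.**

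| Effect in 13.2 | Described instrument | By-arm analysis in 7.26 |
|---|---|---|
| Irregular bleeding | none | none |
| Premenstrual syndrome | none | none |
| Headache or migraine | none | none |
| Breast symptoms | none | none |
| Nausea or vomiting | none | none |
| Abdominal symptoms | none | none |
| Mood changes | GAD-7, BDI-II (months 3 and 6) | chi-square on anxiety and depression |

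Six of the seven have neither, including the only one predicted to differ by arm.

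**2. Size of the gap.** Inputs are the 13.2 rates and the target in section 9.1, which expects to "enroll 30 participants into the cyclical OCP group and another 30 participants into the continuous 6 month OCP group". Assumptions: the rates apply over the six months, equally in both arms, with no dropout. Expected count = n × rate.

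| Effect | Rate | Per arm (n = 30) | Both arms (n = 60) |
|---|---|---|---|
| Premenstrual syndrome | 0.132 | 3.96 | 7.92 |
| Headache or migraine | 0.107 | 3.21 | 6.42 |
| Breast symptoms | 0.083 | 2.49 | 4.98 |
| Nausea or vomiting | 0.045 | 1.35 | 2.70 |
| Abdominal symptoms | 0.023 | 0.69 | 1.38 |
| **Sum without mood** | **0.390** | **11.70** | **23.40** |

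Mood would add 60 × 0.023 = 1.38, giving 24.78, but it has instruments and is left out. The 23.4 counts each effect separately; one woman can contribute to several rows. Irregular bleeding comes on top and cannot be counted, because no rate is given.

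**3. What 30 per arm could show if the data were collected.** Two-sided alpha of 0.05 is assumed. With p̄ the mean of p₁ and p₂,

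power = Φ{ [ |p₂ − p₁|√n − 1.96√(2p̄(1 − p̄)) ] / √(p₁(1 − p₁) + p₂(1 − p₂)) }.

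For a doubling of premenstrual syndrome, p₁ = 0.132, p₂ = 0.264, p̄ = 0.198:

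(0.132 × 5.477 − 1.96 × 0.5636) / 0.5558 = −0.687, so power is 0.246.

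The same formula gives 0.20 for headache, 0.16 for breast symptoms, 0.10 for nausea and 0.07 for abdominal symptoms. Power of 80% for a doubling would need 142 per arm (premenstrual syndrome) to 988 per arm (abdominal symptoms).

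For irregular bleeding, I assume 10%, 20% or 30% in the cyclical arm. Power of 80% at 30 per arm then needs 40.9%, 54.3% or 65.5% in the continuous arm. The 95% interval half-width is 1.96√{[p₁(1 − p₁) + p₂(1 − p₂)]/30}:

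- 10% against 20%: 1.96√(0.25/30) = 0.179
- 20% against 40%: 1.96√(0.40/30) = 0.226
- 30% against 50%: 1.96√(0.46/30) = 0.243

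So a bleeding difference would be estimated to within about 18 to 24 percentage points either way.

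**The case against.** A reader might infer that the plan collects nothing on tolerability and that the rule in 14.2 discards ordinary side effects. The documents do not support either reading.

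- **Mood is covered.** GAD-7 and BDI-II are given at months 3 and 6 and the arms are compared.
- **The 14.2 rule is about reporting.** It decides which events go to the IRB and how fast. It does not say that other events go unrecorded, and a serious event meets it even when expected. What is true is that it is the only adverse event criterion stated, and nothing requires the remaining events to be recorded.
- **Other routes exist.** The month 3 specialist visit and informal contact, the month 6 exam, participant-initiated contact, the two-weekly chart review and the adverse event discussions could each bring a side effect to light. Lipids at month 3 and vitals at month 6 also bear on two of the less likely effects. But no route has a described symptom list or event form, and the chart review is mainly a check that study procedures are done on time.
- **Some documents are not visible.** The items of the REDCap follow-up and PCOS quality-of-life questionnaires are not reproduced, and the full procedure table is a separate attachment. A bleeding or symptom item cannot be ruled out; one can say only that none is described.
- **Tolerability is not among the four aims, and the trial is too small to test it.** Both points stand. They limit what can be claimed from the data but do not argue against collecting it: estimating rates by arm is a proper use of a pilot, and reasons for missed pills bear directly on Aim 1.

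**Conclusion.** The point holds as a gap in systematic recording. Six of the seven anticipated common effects, including the only one predicted to differ between arms, have no described instrument and no planned comparison. About 23 non-mood side-effect reports among 60 women, plus all irregular bleeding, would depend on unstructured reporting in an open-label trial. That figure assumes the 13.2 rates apply over six months with no dropout, and it scales directly with those rates. The bleeding component cannot be sized from the documents.

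The consequence is that the pilot could not give a fair tolerability comparison or explain missed pills and drop-out. It does not undermine the hormone or skin comparisons. The conclusion would fall away in part or whole if the questionnaires not shown already ask about bleeding and symptoms. This is a worthwhile, inexpensive improvement.

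**What to change.** First check the REDCap month 3 and month 6 follow-up questionnaires. If they do not already contain these items:

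1. Add one short checklist, worded identically for both arms, at the month 1 visit and in the existing month 3 and month 6 questionnaires, ideally also at baseline.
2. Cover bleeding and spotting days since the last visit, each likely side effect in 13.2 (yes or no, with severity), and whether pills were skipped or stopped because of it. State in advance what counts as irregular bleeding, since the cyclical arm also has withdrawal bleeding in the placebo week.
3. Record every reported event, whatever its expectedness, and leave the 14.2 rule to govern IRB reporting.
4. Add to 7.26 a descriptive table of counts and proportions by arm, with 95% confidence intervals for the differences, and state that no powered test is intended.

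The cost is a few survey items, one table and a few minutes per participant, with no new visit or test. Solicited questions will produce higher rates of minor events than spontaneous reporting, so the results should not be set against spontaneously reported rates. Recall will be imprecise over the gaps between contacts: 8 weeks from week 4 to week 12, and 12 weeks from week 12 to week 24.
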